#### **10.1.7.1 Definition of an Overdose for This Protocol and Reporting of Overdose to the Sponsor**

The subject has taken (accidentally or intentionally) any drug administered as part of the protocol and exceeding the dose as prescribed by the protocol. It is up to the Investigator or the reporting physician to decide whether a dose is to be considered an overdose, in consultation with the Sponsor.

If an adverse event(s) is associated with (“results from”) the overdose of Sponsor's product or vaccine, the adverse event(s) is reported as a serious adverse event, even if no other seriousness criteria are met.

If a dose of Sponsor's product or vaccine meeting the protocol definition of overdose is taken without any associated clinical symptoms or abnormal laboratory results, the overdose is reported as a non-serious Event of Clinical Interest (ECI), using the terminology “accidental or intentional overdose without adverse effect.”

All reports of overdose with or without an adverse event must be reported by the Investigator within 24 hours to the Sponsor either by electronic media or paper. Electronic reporting procedures can be found in the EDC data entry guidelines. Paper reporting procedures can be found in the Investigator Trial File Binder (or equivalent).

#### **10.1.7.2 Reporting of Pregnancy and Lactation to the Sponsor**

Although pregnancy and lactation are not considered adverse events, it is the responsibility of Investigators or their designees to report any pregnancy or lactation in a subject (spontaneously reported to them) that occurs during the trial.

Pregnancies and lactations that occur after the consent form is signed but before allocation must be reported by the Investigator if they cause the subject to be excluded from the trial, or are the result of a protocol-specified intervention, including but not limited to washout or discontinuation of usual therapy, diet, treatment or a procedure. Pregnancies and lactations that occur from the time of allocation through 14 days following cessation of Sponsor's product must be reported by the Investigator. All reported pregnancies must be followed to the completion/termination of the pregnancy. Pregnancy outcomes of spontaneous abortion, missed abortion, benign hydatidiform mole, blighted ovum, fetal death, intrauterine death, miscarriage and stillbirth must be reported as serious events (Important Medical Events). If the pregnancy continues to term, the outcome (health of infant) must also be reported.

Such events must be reported within 24 hours to the Sponsor either by electronic media or paper. Electronic reporting procedures can be found in the EDC data entry guidelines. Paper reporting procedures can be found in the Investigator Trial File Binder (or equivalent).

### 10.1.7.3 Immediate Reporting of Adverse Events

#### 10.1.7.3.1 Serious Adverse Events

A serious adverse event is any adverse event occurring at any dose or during any use of Sponsor's product that has the following outcome:

- Death
- Immediately life threatening
- Persistent or significant disability/incapacity
- Inpatient hospitalization or prolongation of hospitalization
- Congenital anomaly/birth defect
- Other important medical event

Note: In addition to the above criteria, adverse events meeting either of the below criteria, although not serious per ICH definition, are reportable to the Sponsor in the same timeframe as serious adverse events to meet certain local requirements. Therefore, these events are considered serious by the Sponsor for collection purposes.

- Cancer
- Overdose

Refer to [Table 1](#) for additional details regarding each of the above criteria.

For the time period beginning when the consent form is signed until treatment allocation, any serious adverse event, or follow up to a serious adverse event, including death due to any cause, that occurs to any subject must be reported within 24 hours to the Sponsor if it causes the subject to be excluded from the trial, or is the result of a protocol-specified intervention, including but not limited to washout or discontinuation of usual therapy, diet, treatment or a procedure.

For the time period beginning at treatment allocation through 14 days following cessation of treatment, any serious adverse event, or follow up to a serious adverse event, including death due to any cause, whether or not related to the Sponsor's product, must be reported within 24 hours to the Sponsor either by electronic media or paper. Electronic reporting procedures can be found in the EDC data entry guidelines. Paper reporting procedures can be found in the Investigator Trial File Binder (or equivalent).

Additionally, any serious adverse event, considered by an Investigator who is a qualified physician to be related to the Sponsor's product that is brought to the attention of the Investigator at any time outside of the time period specified in the previous paragraph also must be reported immediately to the Sponsor.

All subjects with serious adverse events must be followed up for outcome.

### 10.1.7.3.2 Events of Clinical Interest

Selected non-serious and serious adverse events are also known as ECI and must be reported to the Sponsor.

For the time period beginning when the consent form is signed until treatment allocation, any ECI, or follow up to an ECI, that occurs to any subject must be reported within 24 hours to the Sponsor if it causes the subject to be excluded from the trial, or is the result of a protocol-specified intervention, including but not limited to washout or discontinuation of usual therapy, diet, treatment or a procedure.

For the time period beginning at treatment allocation through 14 days following cessation of treatment, any ECI, or follow up to an ECI, whether or not related to the Sponsor's product, must be reported within 24 hours to the Sponsor, either by electronic media or paper. Electronic reporting procedures can be found in the EDC data entry guidelines. Paper reporting procedures can be found in the Investigator Trial File Binder (or equivalent).

Events of clinical interest for this trial include:

- an overdose of Sponsor's product, as defined in [Section 10.1.7.1](#) that is not associated with clinical symptoms or abnormal laboratory results.
- an elevated AST or ALT laboratory value that is greater than or equal to three times (3X) the upper limit of normal (ULN) and an elevated total bilirubin laboratory value that is greater than or equal to 2X the ULN and, at the same time, an alkaline phosphatase laboratory value that is less than 2X the ULN, as determined by way of protocol-specified laboratory testing or unscheduled laboratory testing.\*

\*Note: These criteria are based upon available regulatory guidance documents. The purpose of the criteria is to specify a threshold of abnormal hepatic tests that may require an additional evaluation for an underlying etiology. The trial site guidance for assessment and follow up of these criteria can be found in the Investigator Trial File Binder or equivalent.

### 10.1.7.4 Evaluating Adverse Events

An Investigator who is a qualified physician will evaluate all adverse events with respect to the elements outlined in [Table 1](#). The Investigator's assessment of causality is required for each adverse event. Refer to [Table 1](#) or instructions in evaluating adverse events.

**Table 1: Evaluating Adverse Events**

Maximum Intensity (Severity)	Mild	awareness of sign or symptom, but easily tolerated (for pediatric trials, awareness of symptom, but easily tolerated)
	Moderate	discomfort enough to cause interference with usual activity (for pediatric trials, definitely acting like something is wrong)
	Severe	incapacitating with inability to work or do usual activity (for pediatric trials, extremely distressed or unable to do usual activities)
Seriousness	A serious adverse event is any adverse event occurring at any dose or during any use of Sponsor's product that:	
	† Death ; or	
	† Immediately life threatening ; or places the subject, in the view of the Investigator, at immediate risk of death from the event as it occurred [Note: This does not include an adverse event that, had it occurred in a more severe form, might have caused death.]; or	
	† Persistent or significant disability/incapacity (substantial disruption of one's ability to conduct normal life functions); or	
	† Inpatient hospitalization or prolongation of hospitalization (hospitalization is defined as an inpatient admission, regardless of length of stay, even if the hospitalization is a precautionary measure for continued observation. (Note: Hospitalization [including hospitalization for an elective procedure] for a preexisting condition which has not worsened does not constitute a serious adverse event.); or	
	† Congenital anomaly/birth defect (in offspring of subject taking the product regardless of time to diagnosis); or	
	Cancer ; or	
	Overdose (whether accidental or intentional). Any adverse event associated with an overdose is considered a serious adverse event. An overdose that is not associated with an adverse event is considered a non-serious ECI and must be reported within 24 hours.	
	Other important medical event that may not result in death, not be life threatening, or not require hospitalization may be considered a serious adverse event when, based upon appropriate medical judgment, the event may jeopardize the subject and may require medical or surgical intervention to prevent one of the outcomes listed previously (designated above by a †).	
Duration	None	
	Record the start and stop dates of the adverse event. If less than 1 day, indicate the appropriate length of time and units.	
Action Taken	The action taken is in reference to the either the Sponsor's Product or the Interacting Drug. Did the adverse event cause the Sponsor's product or the Interacting Drug to be:	
	None	
	Reduced	
	Interrupted	
	Discontinued	
	Increased	
	Not Applicable	
	Unknown	

Relationship to Sponsor's Product	Did the Sponsor's product cause the adverse event? The determination of the likelihood that the Sponsor's product caused the adverse event will be provided by an Investigator who is a qualified physician. The Investigator's signed/dated initials on the source document or worksheet that supports the causality noted on the adverse event form, ensures that a medically qualified assessment of causality was done. This initialled document must be retained for the required regulatory time frame. The criteria below are intended as reference guidelines to assist the Investigator in assessing the likelihood of a relationship between the test drug and the adverse event based upon the available information.
	The following components are to be used to assess the relationship between the Sponsor's product and the adverse event; the greater the correlation with the components and their respective elements (in number and/or intensity), the more likely the Sponsor's product caused the adverse event:
Exposure	Is there evidence that the subject was actually exposed to the Sponsor's product such as: reliable history, acceptable compliance assessment (pill count, diary, etc.), expected pharmacologic effect, or measurement of drug/metabolite in bodily specimen?
Time Course	Did the adverse event follow in a reasonable temporal sequence from administration of the Sponsor's product? Is the time of onset of the adverse event compatible with a drug-induced effect (applies to trials with investigational medicinal product)?
Likely Cause	Is the adverse event not reasonably explained by another etiology such as underlying disease, other drug(s)/vaccine(s), or other host or environmental factors
Dechallenge	Was the Sponsor's product discontinued or dose/exposure/frequency reduced? If yes, did the adverse event resolve or improve? If yes, this is a positive dechallenge. If no, this is a negative dechallenge. (Note: This criterion is not applicable if: (1) the adverse event resulted in death or permanent disability; (2) the adverse event resolved/improved despite continuation of the Sponsor's product; (3) the trial is a single-dose drug trial; or (4) Sponsor's product(s) is/are only used one time.)
Rechallenge	Was the subject re-exposed to the Sponsor's product in this trial? If yes, did the adverse event recur or worsen? If yes, this is a positive rechallenge. If no, this is a negative rechallenge. (Note: This criterion is not applicable if: (1) the initial adverse event resulted in death or permanent disability, or (2) the trial is a single-dose drug trial; or (3) Sponsor's product(s) is/are used only one time.) NOTE: IF A RECHALLENGE IS PLANNED FOR AN ADVERSE EVENT WHICH WAS SERIOUS AND WHICH MAY HAVE BEEN CAUSED BY THE SPONSOR'S PRODUCT, OR IF RE-EXPOSURE TO THE SPONSOR'S PRODUCT POSES ADDITIONAL POTENTIAL SIGNIFICANT RISK TO THE SUBJECT THEN THE RECHALLENGE MUST BE APPROVED IN ADVANCE BY THE U.S. CLINICAL MONITOR AND THE INSTITUTIONAL REVIEW BOARD/INDEPENDENT ETHICS COMMITTEE.
Consistency with Trial Treatment Profile	Is the clinical/pathological presentation of the adverse event consistent with previous knowledge regarding the Sponsor's product or drug class pharmacology or toxicology?
The assessment of relationship will be reported on the case report forms /worksheets by an Investigator who is a qualified physician according to his/her best clinical judgment, including consideration of the above elements.	
Record one of the following:	Use the following scale of criteria as guidance (not all criteria must be present to be indicative of a Sponsor's product relationship).

Related (there is a reasonable possibility of Sponsor's product relationship)	There is evidence of exposure to the Sponsor's product. The temporal sequence of the adverse event onset relative to the administration of the Sponsor's product is reasonable. The adverse event is more likely explained by the Sponsor's product than by another cause.
Not Related (there is not a reasonable possibility of Sponsor's product relationship)	Subject did not receive the Sponsor's product OR temporal sequence of the adverse event onset relative to administration of the Sponsor's product is not reasonable OR there is another obvious cause of the adverse event. (Also entered for a subject with overdose without an associated adverse event.)

### 10.1.7.5 Sponsor Responsibility for Reporting Adverse Events

All adverse events will be reported to regulatory authorities, IRB or independent ethics committees (IECs), and Investigators in accordance with all applicable global laws and regulations i.e., per ICH Topic E6 (R1) Guidelines for Good Clinical Practice.

## 10.2 Pharmacokinetic Assessment

### 10.2.1 Blood Sampling and Processing

For all subjects, blood samples for the determination of MK-3866 will be collected at scheduled time points as delineated in the Study Events Flow Chart ([Section 6](#)).

Instructions for blood sampling, collection, processing, and sample shipment for MK-3866 will be provided separately.

Blood collections outside the following windows will be considered deviations:

Hour	Deviation window
0 to 1 hour	± 5 minutes
> 1 to < 24 hour	± 15 minutes
≥ 24 hour	± 30 minutes

### 10.2.2 Urine Collection

Prior to the predose sample, each subject will be instructed as to urine collection methods.

Urine samples for determination of MK-3866 concentrations will be collected over selected intervals as outlined in the Study Events Flow Chart ([Section 6](#)). For subjects with mild, moderate, and severe RI, and subjects with ESRD, urine samples will be collected whenever possible, as subjects may not be able to produce urine within each interval. For subjects who are anuric, urine samples for urinalysis will not be collected.

On Day 1, a spot collection will be obtained prior to dosing for the pre-dose sample. Subjects will be asked again to empty their bladder within approximately 15 minutes prior to dosing, and no urine will be collected at this time unless it is needed for the pre-dose sample. Only one predose urine sample will be collected on Day 1.

After administration of MK-3866, during the 24 hour period, all urine will be collected completely. Urine portions will be pooled per subject within any planned collection interval. Just prior to the end of each sampling interval, subjects will be encouraged to void their bladder again to complete the collection. If they void at any time during the collection interval, the time should be documented. Should this be the case, subjects need to attempt to void again at the end of the collection period, as scheduled. However, should subjects be unable to void, this will be documented as well.

Urine will be refrigerated during the collection intervals. The weight of an empty urine collection container and total weight of urine collected during each timed interval will be recorded.

Instructions for urine collection, processing, and sample shipment for MK-3866 will be provided separately.

#### **10.2.3 Dialysate Collection (Part 2 only)**

For ESRD subjects only, dialysate samples will be collected at scheduled time points as delineated in the Study Events Flow Chart ([Section 6](#)).

Instructions for dialysate sampling, collection, processing, and sample shipment for MK-3866 will be provided separately.

#### **10.3 Planned Genetic Analysis Sample Collection**

Sample collection, storage and shipment instructions for Planned Genetic Analysis samples will be provided separately.

#### **10.4 Future Biomedical Research Samples**

The following specimens are to be obtained as part of Future Biomedical Research:

- DNA for future research

## 10.5 Blood Volume Drawn for Study Assessments

**Table 2: Blood Volume Drawn During the Study in Part 1**

Sample Type	Number of Time Points	Approximate Volume per Time Point * (mL)	Approximate Sample Volume Over Course of Study (mL)
Screening laboratory safety tests (including hematology, serum chemistry, serology), FSH (for postmenopausal female subjects only) and serum pregnancy (for female subjects only).	1	12.5	12.5
Blood for Planned Genetic Analysis	1	8.5	8.5
On-study hematology and serum chemistry (including serum pregnancy for female subjects only when scheduled at the same time)	3	12.5	37.5
Blood for MK-3866 (healthy subject)	13	6	78
Blood for MK-3866 (subject with mild or moderate RI)	15	6	90
Blood for MK-3866 (subject with severe RI)	17	6	102
Total Blood Volume Healthy Subject (mL)→			136.5 §
Total Blood Volume Subject with Mild or Moderate RI (mL)→			148.5 §
Total Blood Volume Subject with Severe RI (mL)→			160.5 §

\* Represents the largest collection tube that may be used for this (a smaller tube may be used).

§ If additional safety or pharmacokinetic analysis is necessary or if larger collection tubes are required to obtain sufficient plasma/serum for analysis, additional blood may be obtained (up to a maximum of 50 mL).

**Table 3: Blood Volume Drawn During the Study in Part 2**

Sample Type	Number of Time Points	Approximate Volume per Time Point * (mL)	Approximate Sample Volume Over Course of Study (mL)
Screening laboratory safety tests (including hematology, serum chemistry, serology), FSH (for postmenopausal female subjects only) and serum pregnancy (for female subjects only).	1	12.5	12.5
Blood for Planned Genetic Analysis	1	8.5	8.5
On-study hematology and serum chemistry (including serum pregnancy for female subjects only when scheduled at the same time)	7	12.5	87.5
Blood for MK-3866	47	6	282
Total Blood Volume (mL)→			390.5 §

\* Represents the largest collection tube that may be used for this (a smaller tube may be used).

§ If additional safety or pharmacokinetic analysis is necessary or if larger collection tubes are required to obtain sufficient plasma/serum for analysis, additional blood may be obtained (up to a maximum of 50 mL).

## 11 DATA ANALYSIS

### 11.1 Pharmacokinetic Parameters

#### 11.1.1 Plasma

For all subjects, the following pharmacokinetic parameters for plasma MK-3866 will be calculated as appropriate:

AUC 0-∞ :	Area under the concentration versus time curve from 0 to infinity after single dosing
AUC 0-last :	Area under the concentration versus time curve, from 0 to the time of the last quantifiable (above LLOQ) sample
AUC 0-24 :	Area under the concentration versus time curve, from 0 to 24 hours after dosing
C eoi :	Concentration at end of infusion
C max :	Maximum observed plasma concentration after the administration of a given dose.
CL:	Clearance
T max :	Time to maximum observed plasma drug concentration
t ½ :	Elimination terminal half-life
V d :	Volume of distribution

No value for AUC0-∞, CL, Vd, or elimination terminal t½, will be reported for cases that do not exhibit a terminal log-linear phase in the concentration versus time profile.

No values for pharmacokinetic parameters will be estimated for subjects with 2 or fewer consecutive time points with detectable concentrations.

Individual and mean plasma concentration time curves (both linear and log-linear) will be included in the final report.

### 11.1.2 Urine

For all subjects, values for the following pharmacokinetic parameters for urine MK-3866 will be estimated as appropriate:

Ae0-24: Total amount of drug excreted unchanged in the urine over the period of 24 hours, obtained by adding the amounts excreted over each collection interval

CLR: Renal clearance calculated as  $Ae(t'-t'')/AUC(t'-t'')$  where  $t'-t''$  is the longest interval of time during which Ae and AUC are both obtained

Fe: Fraction of MK-3866 excretion during each collection interval. Obtained by dividing the amount of MK-3866 excreted in each collection interval by the dose

### 11.1.3 Hemodialysis: Plasma and Dialysate

For subjects in Panel E, the following pharmacokinetic parameters for plasma MK-3866 will be calculated as appropriate:

Ca: Concentration in plasma entering the dialyzer line (arterial or pre-dialyzer line)

Cv: Concentration in plasma exiting the dialyzer (venous or post-dialyzer line)

AUCD: Plasma AUC values determined from Ca versus time profile during the dialysis period (0.5-4.5 hours) using 'linear up, log down' calculation method option in WinNonlin

AUC(1-4.5)Ca: Plasma AUC values determined from Ca versus time profile during the dialysis period from 1 hour to 4.5 hours using 'linear up, log down' calculation method option in WinNonlin

AUC(1-4.5)Cv: Plasma AUC values determined from Cv versus time profile during the dialysis period from 1 hour to 4.5 hours using 'linear up, log down' calculation method option in WinNonlin

CLD,plasma: Dialysis clearance based on plasma, calculated as  $Q \times R \times (AUC[1-4.5]Ca - AUC[1-4.5]Cv) / AUC(1-4.5)Ca$ , where Q is the flow rate of blood through the dialyzer, and R is the ratio of blood drug concentration to plasma drug concentration

For subjects in Panel E, the following pharmacokinetic parameters for dialysate MK-3866 will be calculated as appropriate:

CD:	Concentration in dialysate samples
AD:	Amount of drug recovered from each dialysate collection, calculated as: CD x dialysate volume
rr:	Rate of drug removal, calculated as: (CD x dialysate flow rate)
AD,total:	Cumulative amount of drug recovered from the dialysate will be obtained by integrating the rr versus time profile over the dialysis session duration, using actual times relative to the start time of dialysis
CLD,dialysate:	HD clearance based on dialysate, calculated as: AD,total/AUCD

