- q. During HD, blood samples for MK-3866 will be collected from both the pre-dialyzer and post-dialyzer blood lines; thus 2 plasma samples per time point during HD will be taken. A blood sample (a pre-dialyzer and post-dialyzer) will also be obtained immediately before the HD is stopped, if this time point does not coincide with a time point that is already scheduled.
- r. Dialysate samples for determination of MK-3866 will be obtained pre-dialysis, post-dialysis (before the HD is stopped), and for 1 minute every half hour during HD.
- s. HD session will be initiated immediately following the 0.5-hour postdose blood draw.

Abbreviations: ConMed = Concomitant Medication, CRU = Clinical Research Unit, FU = Follow-Up, FSH = Follicle Stimulating Hormone, HIV = Human Immunodeficiency Virus, IV = Intravenous, HD = Hemodialysis P = Predose, RI = Renal Impairment, S = Screening, UA = Urinalysis

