#### **10.1.5 Hemodialysis (ESRD Subjects Only)**

ESRD subjects on HD will receive HD as per their regular schedule and blood and dialysate sampling be collected as outlined in the Study Events Flow Chart ([Section 6](#)).

Dosing in Period 1 will occur immediately following completion of a normally scheduled HD session. For subjects following a Monday, Wednesday, Friday HD schedule, MK-3866 will be administered immediately following their Friday HD session. For subjects following a Tuesday, Thursday, Saturday HD schedule, MK-3866 will be administered immediately following their Saturday HD session. The 72-hour HD (either Monday or Tuesday) should initiate immediately following the 72-hour blood draw. If HD must be initiated prior to 72 hours postdose, a sample for MK-3866 analysis will be collected prior to HD, and the time recorded.

Dosing in Period 2 will occur approximately 30 minutes prior to the normally scheduled HD session. For subjects following a Monday, Wednesday, Friday HD schedule, MK-3866 will be administered prior to their Friday HD session. For subjects following a Tuesday, Thursday, Saturday HD schedule, MK-3866 will be administered prior to their Saturday HD

session. The subsequent HD session should initiate immediately following the 30 minute blood draw.

In Period 2, the HD period will be approximately 4 hours for all subjects. Blood samples collected during HD will be collected from both the pre-dialyzer and post-dialyzer blood lines.

The blood flow, dialysate flow, and the make and model of the dialyzer will be recorded.

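### CLD,dialysate divides drug recovered over the actual dialysis session by a plasma AUC with printed limits of 0.5-4.5 h, so a subject's value is generally off when the session starts or stops at other times

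*Combined protocol and SAP*

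**What the plan says.** Section 11.1.3 gives the dialysate-based clearance as "HD clearance based on dialysate, calculated as: AD,total/AUCD".

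- **Numerator.** AD,total is obtained by "integrating the rr versus time profile over the dialysis session duration, using actual times relative to the start time of dialysis".
- **Denominator.** AUCD is the AUC of Ca (plasma entering the dialyzer) "during the dialysis period (0.5-4.5 hours", with the clock starting at the start of infusion.

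The rest of the protocol makes the session times approximate:

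- Section 10.1.5: "In Period 2, the HD period will be approximately 4 hours for all subjects".
- Section 6.2, footnote s: "HD session will be initiated immediately following the 0.5-hour postdose blood draw". Footnote l puts that draw at the end of the infusion, and section 9.4.1 lets the infusion run 30 ± 5 minutes.
- Section 6.2, footnote q: a further pair of pre- and post-dialyzer samples is taken "immediately before the HD is stopped, if this time point does not coincide with a time point that is already scheduled".

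CLD,plasma, also in section 11.1.3, uses AUC(1-4.5)Ca and AUC(1-4.5)Cv in the numerator and AUC(1-4.5)Ca in the denominator.

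**The concern.** A clearance computed as amount over AUC is meaningful only if both cover the same interval. Here one interval follows the subject and the other, as printed, does not. The plan applies the matching principle to renal clearance in section 11.1.2, where the amount excreted and the AUC must come from a common interval. It does not carry that principle over to dialysis clearance.

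Read literally, a session that runs past 4.5 h keeps adding drug to the numerator while the denominator stops. A session that ends early leaves off-dialysis exposure in the denominator. How much drug dialysis removes is secondary objective 1 (section 8.1.2), and section 7.2.1 names dosing recommendations with respect to dialysis as a purpose of the study. With 8 subjects, an artefact of session timing adds avoidable error and spread to one of the parameters that describe removal.

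**Working it through.** **1. The printed window.** Planned start 0.5 h plus planned duration 4 h gives 4.5 h, so AUCD's limits are the nominal session. A session that keeps exactly to plan has no mismatch.

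**2. Form of the error.** If dialysis clearance is constant, AD,total = CLD × AUC(actual start to actual stop). Hence

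reported/true CLD,dialysate = AUC(actual session) / AUC(0.5-4.5 h).

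**3. Assumed inputs.** The documents give no half-life on dialysis, so I take 2, 3 and 4 h. They give no observed half-life off dialysis either. A rough value follows from the projections in section 7.2.2 (AUC0-∞ 202 μM·hr, Ceoi 24 μM) under mono-exponential decline: ln 2 × 202/24 = 5.8 h. Removing the exposure during the infusion (0.25 × 24 = 6) gives ln 2 × 196/24 = 5.7 h, which makes no practical difference below.

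**4. Session starting at 0.5 h.** Scale the concentration at 0.5 h to 1 and write A(k, d) = (1 − e^(−kd))/k, with k_on = ln 2/(half-life on dialysis) and k_off = ln 2/5.8.

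- Session of d < 4 h: ratio = A(k_on, d) / [A(k_on, d) + e^(−k_on·d) × A(k_off, 4 − d)]
- Session of d > 4 h: ratio = A(k_on, d) / A(k_on, 4)

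At a 3 h half-life on dialysis:

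- 3.5 h session: 2.400/2.616 = 0.917
- 4.5 h session: 2.798/2.611 = 1.072

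| Half-life on dialysis | 3.5 h | 3.75 h | 4.25 h | 4.5 h |
|---|---|---|---|---|
| 2 h | 0.934 | 0.969 | 1.028 | 1.053 |
| 3 h | 0.917 | 0.960 | 1.037 | 1.072 |
| 4 h | 0.908 | 0.955 | 1.042 | 1.083 |

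**5. Late start.** A session of exactly 4 h that starts 10 minutes late gives 0.945, 0.963 and 0.972 for half-lives of 2, 3 and 4 h.

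**6. Cancellation.** Within one subject, a 10-minute late start with a 4.5 h session at a 2 h half-life gives 0.995. Across subjects at a 3 h half-life, equal numbers of sessions 15 minutes short and 15 minutes long average (0.960 + 1.037)/2 = 0.9985. At 30 minutes the average is (0.917 + 1.072)/2 = 0.9945.

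**7. After the change.** With AUCD taken from actual start to actual stop, the two AUCs in step 2 are the same, and the ratio is 1.00 for any start time or length under constant clearance.

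**8. CLD,plasma.** The formula is Q × R × (AUC Ca − AUC Cv)/AUC Ca, with every AUC over 1-4.5 h. Nothing is mismatched. If dialysis starts by 1 h and runs past 4.5 h, the window lies wholly inside the session. If dialysis stops before 4.5 h, no post-dialyzer plasma exists for the remainder, and the plan does not say how to end the two AUCs.

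**The case against.** The best defence is that the printed hours are only the nominal label of the dialysis period. Ca is by definition plasma entering the dialyzer, so it stops existing when dialysis stops. The parameters are computed as appropriate, and footnote q supplies a true end sample. An analyst could then use actual times without departing from the text.

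Part of this stands. For a short session, the understatement arises only if someone carries AUCD on to 4.5 h with a later systemic sample or an extrapolation. But the defence does not cover a long session: Ca is then available past 4.5 h, and the printed limit cuts it off while the numerator continues. The explicit mention of actual times for AD,total, and its absence for AUCD, also favours the literal reading. No sentence elsewhere resolves it.

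Three stronger conclusions that a reader might draw are not supported:

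- **That the value is biased whenever the session departs from the window.** Start and length deviations can offset each other (step 6), and nothing in the documents suggests sessions will run systematically short or long. With balanced deviations the effect is mostly subject-level scatter.
- **That both dialysis clearances are mismatched.** CLD,plasma uses one window throughout (step 8).
- **That the study's main comparisons are affected.** Section 11.2.3.3 gives CLD,dialysate only listings and descriptive statistics. The model-based HD versus non-HD comparison there uses AUC0-∞, AUC0-last, Ceoi (Cmax) and CL, and the primary analysis in section 11.2.3.2 does not use AUCD. No dosing rule in the documents is tied to CLD,dialysate.

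**Conclusion.** As printed, CLD,dialysate pairs an amount from the actual session with an AUC between fixed limits, and a subject's value is generally off when actual dialysis start or stop differs from 0.5 h or 4.5 h. For a session starting at 0.5 h, the understatement is about 7-9% if it lasts 3.5 h and the overstatement about 5-8% if it lasts 4.5 h. At 15 minutes short or long, the errors are about 3-5% down and 3-4% up.

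These sizes rest on constant dialysis clearance, mono-exponential decline and assumed half-lives of 2-4 h on dialysis and about 5.8 h off it. The short-session figures also assume that AUCD is carried to 4.5 h. Actual session lengths are unknown. In the group mean, deviations in both directions partly cancel. This is a minor defect in a descriptive secondary parameter, worth correcting because the correction is free.

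**What to change.** In section 11.1.3:

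- Define AUCD from each subject's actual dialysis start to actual dialysis stop, with the pre-dialyzer sample of the pair taken just before dialysis is stopped (section 6.2, footnote q) as the last point.
- End AUC Ca and AUC Cv for CLD,plasma at the earlier of 4.5 h and actual dialysis stop, using the same end point for both.

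The cost is a few words. The end-of-dialysis samples are already planned, and AD,total already needs the actual session times. No visit, sample or dialysis procedure changes. Making the change before the data are analysed is cleaner than handling it later, because section 11.2 requires changes made after the study has begun to be listed and explained in the CSR.
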